12.3.1 Severity

Severity of AEs will be assessed by the investigator as described in [Appendix D](#). AEs not included in the Appendixes will be graded for severity using the followings definitions as seen in [Table 15](#).

Table 15: Definitions for Severity of AE Grading

Severity	Definition
Grade 1 (Mild)	No interference with activity, may use 1 dose of an over the counter medication
Grade 2 (Moderate)	Repeated use of non-narcotic pain reliever > 24 hours or some interference with activity
Grade 3 (Severe)	Activities of daily living limited to <50% of baseline, medical evaluation/therapy required
Grade 4 (Potentially Life-Threatening)	Extreme limitation in activity, significant assistance required; immediate medical

	intervention or therapy required to prevent death
Grade 5	Death

12.3.2 Causality

Causality (likelihood that the event is related to the study agent) will be assessed considering the factors listed under the following categories:

Definitely Related

- reasonable temporal relationship
- follows a known response pattern
- clear evidence to suggest a causal relationship
- there is no alternative etiology

Probably Related

- reasonable temporal relationship
- follows a suspected response pattern (based on similar agents)
- no evidence of a more likely alternative etiology

Possibly Related

- reasonable temporal relationship
- little evidence for a more likely alternative etiology

Unlikely Related

- does not have a reasonable temporal relationship
- OR
- good evidence for a more likely alternative etiology

Not Related

- does not have a temporal relationship
- OR
- definitely due to an alternative etiology

Note: Other factors will also be considered for each causality category when appropriate. Causality assessment is based on available information at the time of the assessment of the AE.

The investigator may revise the causality assessment as additional information becomes available.

The degree of certainty with which an AE can be attributed to administration of the study vaccine will be determined by how well the event can be understood in terms of one or more of the following:

- The event being temporally related with vaccination or reproduced on re-vaccination.
- A reaction of similar nature having previously been observed with this type of vaccine and/or formulation.
- The event having been reported in the literature for similar types of vaccines.
- Whether or not there is another identifiable cause.

All local (injection site) reactions will be considered causally related to vaccination. All malaria cases will be reported as not related to vaccination. Asymptomatic parasitemia (positive blood smears without related malaria clinical symptoms) will not be reported as an AE. Clinical malaria will be reported as an AE.

Reports will further classify AEs as follows:

- Related - all AEs that are assessed as definitely, probably, or possibly related.
- Unrelated - all AEs assessed as unlikely or definitely not related.

When reporting to regulatory authorities and IRBs is needed, AE relationship will be determined as noted above.

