5.2 Study Endpoints

5.2.1 Primary Endpoint

- Incidence of local and systemic AEs and SAEs in Malian adults. (All arms)
- Incidence of local and systemic AEs and SAEs in Malian adults. (Arms 2c, 2d, 4c)

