9.3.1.1 Symptomatic Malaria

Clinical or symptomatic malaria for this study is defined as the presence of asexual *P. falciparum* parasites at any parasitemia with either an axillary temperature of ≥ 37.5 °C or more of the following symptoms: headache, myalgia, arthralgia, malaise, nausea, dizziness, or abdominal pain and will be reported as an AE.

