12.3 Investigator Assessment of Adverse Events

If a diagnosis is clinically evident (or subsequently determined), the diagnosis rather than the individual signs and symptoms or lab abnormalities will be recorded as the AE.

All solicited (see [Table 14](#) below) and unsolicited AEs will be recorded through Day 7 after each vaccination, including injection site reactions, or until resolved. Adverse reactions related to direct skin feeds will be recorded until Day 7 after feeds or until resolved. After that period only unsolicited AEs (including symptomatic malaria), SAEs, UPs, and NOCIs will be recorded. Note that a positive blood smear without associated clinical symptoms will not be reported as an AE.

Table 14: Solicited Adverse Events

Systemic adverse events
Fever (temperature ≥ 38.0 °C)
Headache
Nausea/Vomiting
Diarrhea
Abdominal pain
Fatigue
Myalgia
Arthralgia
Urticaria
Laboratory adverse events
Hemoglobin – decreased hemoglobin
WBC – leukopenia, leukocytosis
ANC/AGC – decreased neutrophil/granulocyte count

Platelet count – thrombocytopenia
ALT – increased ALT
Creatinine (Cr) – increased Cr
Local reactogenicity
Injection pain/tenderness
Injection erythema/redness
Injection swelling
Injection induration
Injection pruritus
Limitation of arm movement

Additional laboratory abnormalities other than those specified as safety labs in the protocol should be reported as adverse events if they require intervention. Interventions include, but are not limited to, discontinuation of treatment, dose reduction/delay, additional assessments, or concomitant treatment. In addition, any medically important laboratory abnormality may be reported as an adverse event at the discretion of the investigator. This could include a laboratory result for which there is no intervention but the abnormal value suggests a disease or organ toxicity. In addition, similar to solicited AEs, all laboratory AEs as defined in [Appendix D](#), will be collected and graded through 7 days after each vaccination or until resolved.

The investigator will evaluate all AEs with respect to Seriousness (criteria listed above), Severity (intensity or grade), and Causality (relationship to study agent and relationship to research) according to the following guidelines.

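### In the week after a vaccination, systemic symptoms in a parasitaemic subject can be recorded as one unsolicited, unrelated malaria AE, losing their solicited and related status and their count

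*Combined protocol and SAP*

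**What the plan says.** Three rules bear on the point.

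- **Diagnosis rule (Section 12.3).** Once a diagnosis is evident, "the diagnosis rather than the individual signs and symptoms or lab abnormalities will be recorded as the AE". No exception is made for the week after a vaccination.
- **Causality rule (Section 12.3.2).** After five graded causality categories, the section adds that "All malaria cases will be reported as not related to vaccination". It also says "Clinical malaria will be reported as an AE", so the event is kept. Section 12.3 classes symptomatic malaria among the unsolicited events.
- **Malaria definition (Section 9.3.1.1).** Asexual "parasites at any parasitemia with either an axillary temperature of" 37.5 °C or above, "or more of the following symptoms: headache, myalgia, arthralgia, malaise, nausea, dizziness, or abdominal pain and will be reported as an AE". As the text reads, the number of symptoms required is missing.

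The next paragraph of Section 12.3 points the other way: solicited (Table 14) as well as "unsolicited AEs will be recorded through Day 7 after each vaccination, including injection site reactions, or until resolved". Nothing says which of the two Section 12.3 rules governs Days 0-7.

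The primary endpoint (Section 5.2.1) covers local and systemic AEs and SAEs without restriction to solicited or related events. Section 14.2 compares the share of subjects with any AE, tabulates AEs by class, severity and relationship, and applies a signed rank test to within-subject differences in 7-day AE counts between the first and later vaccinations.

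**The concern.** A headache, myalgia or fever caused by the vaccine in an adult with incidental parasitaemia meets the definition of clinical malaria, subject to the missing symptom count. If staff follow the diagnosis rule, the reaction becomes one malaria entry and its causality is fixed in advance. Three things are then lost: its place in the solicited and related tables, which carry the reactogenicity part of the primary objective; its multiplicity in the 7-day count; and its contribution to the halting rules in Section 12.9 that require a related event, notably rule 7 (Grade 3 solicited systemic) and rule 9 (Grade 3 unsolicited).

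The effect differs by dose. In the main study, Coartem clearance is given before Vaccination #1 only (Section 15.4.4), so the later doses that are compared with dose 1 are given without it. Section 9.4.4 places the highest parasite carriage after Vaccination #3. Vaccination #4 is open label (Section 5.1.2), so a judgement between malaria and vaccine reaction would be made with the arm known.

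**Working it through.** **1. Overlap of definitions.** Malaria-defining and also in Table 14: headache, myalgia, arthralgia, nausea, abdominal pain. Fever overlaps too. Table 14 starts at 38.0 °C and the malaria definition at 37.5 °C, so, route of measurement aside, any solicited fever in a subject with asexual parasites qualifies. Not malaria-defining: diarrhea and urticaria. Fatigue is not named, although malaise is.

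**2. The plan's own safety figures (Section 14.5).** P(at least one event) = 1 - (1 - p)^n.

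| n | p | Stated | Recomputed |
|---|---|---|---|
| 5 | 0.275 | 0.80 | 0.800 |
| 10 | 0.206 | 0.90 | 0.900 |
| 60 | 0.038 | 0.90 | 0.902 |
| 165 | 0.018 | 0.95 | 0.950 |

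The figures reproduce. They concern any serious or severe AE, so recoding to malaria leaves them unchanged. They would fall only if read as the chance of seeing an event that is recorded as related.

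**3. Assumed recoding share q.** The documents give no value for Days 0-7. I use 10% as a low illustration and 23.7% as the high end: 475 positive of 2005 smears after dose 3 in #15-I-0044 (Table 7, 475/2005 = 0.237). The dose 4 figure printed there is 19.3%. Recoding is taken as independent of the reaction, so the recorded rate is p(1 - q).

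**4. Related events, n = 60, true rate 0.038.** Under the narrower reading in step 2:
- q = 0: 0.902
- q = 10%: 0.038 × 0.90 = 0.0342, giving 0.876
- q = 23.7%: 0.038 × 0.763 = 0.0290, giving 0.829

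**5. Halting rule 7.** Ten percent of 60 is 6 subjects, so the quantity is P(X ≥ 6) with X binomial(60, p(1 - q)). True rate 15%:
- q = 0: 0.903
- q = 10%: rate 0.135, giving 0.837
- q = 19.3%: rate 0.121, giving 0.749
- q = 23.7%: rate 0.114, giving 0.697

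**6. Seven-day count.** Suppose a subject has fever, headache and myalgia after dose 1 (cleared) and again after dose 3 (parasitaemic). Recorded as symptoms, the counts are 3 and 3, difference 0. Under the diagnosis rule they are 3 and 1, difference -2. The signed rank test would read this as fewer AEs with repeat dosing. Because the comparison is within subject, randomisation does not remove it.

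**7. Share with any AE.** One malaria AE still makes the subject a case, so this proportion is unchanged.

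**The case against.** A reader might infer that these reactions disappear from the primary endpoint. They do not: malaria is reported as an AE, the endpoint is not limited to solicited or related events, and step 7 shows one of its comparisons untouched. Nor is replacement certain, since Section 12.3 also requires solicited AEs to be recorded through Day 7. That objection stands in full, and it turns the point into an unresolved conflict between two rules.

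A reader might also multiply smear prevalence into a statement that about one in five reactions is masked, or carry that into a loss of power. The documents do not support either. The Table 7 smears come from feeding periods that began one week after vaccination, mostly outside the solicited window and in another trial. Appendix C lists no smear on Days 1 and 3 after doses 3 and 4, so recoding then depends on a positive smear on the vaccination day or unscheduled testing. Dose 4 is planned before the transmission season (Section 3.5.2.2), so carriage at that point is unknown. The plan claims no power for reactogenicity comparisons.

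The trial's own data suggest that masking is at most partial. Section 3.5.2.1 lists headache, fever, myalgia and arthralgia among related events in the main phase. Section 3.5.2.2 reports no excess of clinical malaria (full versus control p = 0.75, fractional versus control p = 0.87), although that is a check over the whole follow-up and not over Days 0-7. The DSMB has seen unblinded data, and halting criterion 10 covers any safety issue. While blinding held, the rule acted alike in all arms: it shrinks an absolute difference and leaves the expected ratio alone.

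Two practical objections remain. Changing the coding only at dose 4 would harm comparability across doses; this is met if the diagnosis-only count can also be reproduced. Ordinary causality criteria might still return an unlikely rating; that would at least be a case-level judgement.

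**Conclusion.** The conflict is real and should be resolved before dose 4 data are recorded. As written, the plan permits solicited systemic symptoms in Days 0-7 to become one unsolicited, unrelated malaria AE. The proportion with any AE is safe. The solicited and related tables, the 7-day counts across doses and the related-event halting rules are exposed. The exposure is most credible at dose 3. At dose 4 carriage is uncertain, but assessment is open label.

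The size is unknown. The fall in the chance of meeting rule 7, from 0.90 to between 0.84 and 0.70, rests on an assumed 10% to 24% recoding, an assumed true rate of 15%, independence, and a full arm of 60. It shows sensitivity and is not an estimate of what happened.

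**What to change.** - In Section 12.3, state that in Days 0-7 after each vaccination every Table 14 symptom is recorded and graded as a solicited AE whatever the malaria result, and that concurrent malaria is entered as an additional, flagged AE. This settles which rule prevails.
- In Section 12.3.2, have those symptoms assessed by the ordinary causality criteria. The malaria diagnosis itself may stay not related.
- In Section 14.2, report solicited systemic AEs and the 7-day counts with and without malaria-flagged episodes, and also under diagnosis-only coding so that doses remain comparable. Where source records allow, re-tabulate doses 1-3 in the same way.
- In Section 9.3.1.1, supply the missing symptom count.

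This point takes no position on the halting thresholds.

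The cost is a CRF instruction, one extra table and some review of source records. The downside is that some true malaria symptoms will count as solicited AEs, in all arms; the flagged tabulation shows how many. Symptoms not written down at the time may not be recoverable, so the instruction should precede dose 4.

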12.4 Investigator Reporting Responsibilities to the Sponsor

12.4.1 Adverse Events

Line listings, frequency tables and other summary AE data will be submitted to the IND Sponsor when needed for periodic safety reviews, review of IND annual reports, review of IND safety reports, and preparation of final study reports.

12.4.2 Serious Adverse Events

All SAEs (regardless of relationship and whether or not they are also UPs) will be reported on the Safety Expedited Report Form (SERF) and sent to the Sponsor Clinical Safety Office (CSO) by fax or email attachment. Deaths and immediately life-threatening SAEs will be reported within 1 business day after the clinical site becomes aware of the event. All other SAEs will be reported to the CSO within 3 business days after the site becomes aware of the event.

Sponsor Clinical Safety Office Contact Information:

OCRPRO Clinical Safety Office

[name]

[name]

[contact]

[contact]

Email: [contact]

The clinical site Investigator in Mali will also notify LMIV PI and the Site Medical Monitor in Mali by email, fax, or telephone within 1 working day of notification of an SAE occurrence.

LMIV Contact Information:

[name]

[contact]

[contact]

[contact]

12.4.3 Unanticipated Problems

All UPs that are also adverse events will be reported to the CSO on the NIH Problem Report Form sent by fax or email attachment no later than 7 calendar days of site awareness of the event.

UPs that are not AEs will not be reported to the Sponsor CSO.

12.4.4 Pregnancy

Pregnancy itself is not an AE. However, complications of pregnancies are AEs and may be SAEs. Pertinent obstetrical information for all pregnancies will be reported to the CSO and LMIV via fax or email within 3 business days from the site awareness of the pregnancy. All pregnancies will be reported on the Pregnancy Notification/Outcome Form to the CSO.

Pregnancy outcome data (e.g., delivery outcome, spontaneous, or elective termination of the pregnancy) will be reported to the CSO and LMIV within 3 business days of the site's awareness of the outcome on a protocol-specified form.

In the event of pregnancy, the following steps will be taken:

- Discontinuation of the study agent
- Unblind per the site unblinding procedures
- Withdraw from the study but continue in follow-up for safety
- Report to FMPOS Ethics Committee as an informational item

- Report to NIH IRB at time of Continuing Review
- Report to DSMB, Sponsor Medical Monitor, and Site Medical Monitor
- Advise research subject to notify the obstetrician of study vaccine exposure

12.5 Reporting Procedures to the NIH IRB

12.5.1 Expedited Reporting to the NIH IRB

Non-compliance: Any actual or suspected non-compliance by any investigator or entity associated with the protocol must be reported by the NIH PI/designee within 7 calendar days of any investigator or individual associated with the protocol first becoming aware, unless otherwise indicated in this policy.

Non-NIH IRB determinations of serious and/or continuing noncompliance about an NIH investigator: If the NIH is relying on a non-NIH IRB and the Reviewing IRB makes a determination of serious and/or continuing non-compliance regarding an NIH investigator, then, even if the determination has already been provided to OHSRP either directly or via the NIH Institutional Official (IO)/designee, the NIH PI/designee must report this in iRIS within 7 calendar days of any member of the research team being notified of the determination by the Reviewing IRB. The NIH PI must provide the OHSRP office of Compliance and Training with documentation from the Reviewing IRB unless this documentation has already been provided directly to the office by the Reviewing IRB or via the IO.

Major Deviation: A deviation must be reported within 7 calendar days of an investigator becoming aware of an actual or suspected deviation. Although protocol deviations are also non-compliance, these should only be reported once as deviations.

Unanticipated Problem (UP): A UP must be reported within 7 calendar days of an investigator becoming aware of the actual or suspected UP.

Death: Any death of a research subject that is possibly, probably or definitely related to the research must be reported within 24 hours of an investigator becoming aware of the death. New information that might affect the willingness of a subject to enroll or remain in the study should be reported within 7 calendar days of an investigator first becoming aware.

Any suspension or termination of research activities, including holds on new enrollment, placed upon the research by the study sponsor, NIH or IC leadership, or any regulatory agency must be reported within 7 calendar days of an investigator becoming aware.

Investigators must provide the following information to the IRB in summary format at the time of continuing review: Minor protocol deviations; Adverse events and Serious Adverse Events that do not meet the definition of an UP.

Investigators are required to immediately (i.e., no longer than 10 days) report SAEs or UADEs to the study sponsor and, if also an actual or suspected UP, to the IRB within 7 calendar days of an investigator becoming aware.

12.5.2 Annual Reporting to the NIH IRB

All events will be reported to the NIH IRB and FMPOS EC in summary at the time of Continuing Review according to NIH Policy 801.

12.6 Investigator Reporting Responsibilities to the Local IRB

Investigators are responsible for submitting IND Safety Reports and UP summaries that are received from the IND Sponsor to their local IRB/Ethics Committee (FMPOS EC). Investigators must also comply with all local IRB/Ethics Committee (FMPOS EC) reporting requirements, including expedited and annual reporting requirements.

12.7 Follow-up of Adverse Events and Serious Adverse Events

AEs that occur following receipt of a single vaccination are followed until the final outcome is known or until the end of the study follow-up period.

SAEs that have not resolved by the end of the follow-up period will be followed until final outcome is known. If it is not possible to obtain a final outcome for an SAE (e.g., the subject is lost to follow-up), the reason a final outcome could not be obtained will be recorded by the investigator on the AE CRF (if the CRF is still open) and the SERF.

SAEs that occur after the study follow-up period (6 months following the last vaccination) that are reported to and assessed by the Investigator to be possibly, probably, or definitely related must be reported to the CSO as described above.

12.8 Sponsor's Reporting Responsibilities

Serious and unexpected suspected adverse reactions (SUSARs) as defined in 21 CFR 312.32 and determined by the IND Sponsor will be reported to FDA and all participating Investigators as IND Safety Reports.

The IND Sponsor will also submit an IND Annual Report of the progress of the investigation to the FDA as defined in 21 CFR 312.33.

AEs that are also UPs will be summarized by the IND Sponsor and distributed to Investigators.

12.9 Halting Criteria for the Study

The PI will closely monitor study data as they become available and will make determinations regarding the presence and grading of AEs. The AEs will be evaluated with regard to the known complications associated with administration of vaccine components. If a dose of vaccine is considered unacceptably reactogenic (as described in the following criteria), the study will be halted. No new enrollments and no further vaccinations will be administered by the Investigators until reviewed by the DSMB and study IND Sponsor. A report of DSMB recommendations will be submitted to the IRBs. The following criteria will be used to define unacceptable reactogenicity of the malaria vaccine (AEs that are possibly, probably, or definitely related to the vaccine will be considered “related” and will be summarized as such):

1. One or more subjects experience death or any life-threatening SAE, **or**
2. One or more subjects experience an SAE as defined in **Section 12.2** of this protocol that is determined to be possibly, probably, or definitely related to the vaccine, **or**
3. One or more subjects are withdrawn from the study (by investigator or subject request) following a Grade 3 AE that is determined to be possibly, probably, or definitely related to the vaccine, **or**
4. One or more subjects experience a hypersensitivity reaction (e.g. anaphylaxis, diffuse urticaria) that is determined to be possibly, probably, or definitely related to the vaccine, **or**
5. One or more subjects experience any local or solicited AE leading to hospitalization, or fever $>40^{\circ}\text{C}$ (104°F) that is possibly, probably, or definitely related to the vaccine, or necrosis at the injection site, within the 7 days post vaccination, **or**
6. Ten percent or more of subjects in any dose Arm experience any Grade 3 solicited local AE (lasting 48 hours or more) that is determined to be possibly, probably, or definitely related to the vaccine as defined in this protocol, within the 7 days post vaccination, **or**
7. Ten percent or more of subjects in any dose Arm experience any Grade 3 solicited systemic AE (lasting 48 hours or more) that is determined to be possibly, probably, or definitely related to the vaccine as defined in this protocol, within the 7 days post vaccination, **or**
8. Thirty percent or more of subjects in any dose Arm experience the same Grade 2 or higher laboratory abnormality (see **Appendix D**) or ten percent or more experience the same Grade 3 or higher laboratory abnormality regardless of vaccine relationship, within the 7 days post vaccination, **or**
9. Ten percent or more of subjects in any dose Arm experience the same or similar Grade 3 unsolicited AE that is determined to be possibly, probably, or definitely related to the vaccine as defined in this protocol, **or**
10. Any safety issue that the study PI or IND Sponsor determines should halt the study.

If any of these halting criteria are met, request for an unblinded review by the DSMB may be submitted to determine if the safety issues identified were in the comparator or the test vaccines arm of the study.

The IRBs, the NIAID, the FDA, or other government agencies may discontinue the study at any time. Subsequent review of serious, unexpected, and related AEs by the DSMB or IRB, the IND Sponsor, the FDA, and other regulatory authorities may also result in suspension of further administration of vaccine at the clinical site. The FDA, other regulatory authorities, and the study sponsor(s) retain the authority to suspend additional enrollment and administration of vaccine for the entire study as applicable.

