12.10 Halting Criteria for a Subject

The decision to suspend administration of the study agent(s) for a single subject requires discontinuation of study agent administered for the study subject(s) until a decision is made whether or not to continue study agent administration.

The halting criteria for a single subject in this study include:

- A subject experiences an SAE regardless of vaccine relationship, **or**
- A subject experiences ≥ 2 or more Grade 3 or greater AEs (solicited local/systemic or unsolicited; lasting 48 hours or more) that are possibly, probably, or definitely related to the study agent, within the 7 days post vaccination, **or**
- A subject experiences ≥ 2 or more Grade 2 or higher laboratory abnormality (see [Appendix D](#)) or any Grade 3 or higher laboratory abnormality that are possibly, probably, or definitely related to the study agent, within the 7 days post vaccination, **or**

- Any safety issue that the Site Investigator determines should pause administration of the study agent to a single subject or to all subjects in a specific group.

The IND Sponsor, in collaboration with the PI, may also pause for an individual subject or entire group if a safety concern is identified during routine aggregate data analysis.

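### Four study-halting rules stop at Grade 3, so some related Grade 4 reactions count in no fixed rule, and a high symptom-free creatinine without dialysis has no grade

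*Combined protocol and SAP*

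**What the plan says.** Section 12.9 lists ten criteria that halt the study.

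- Item 3 halts on a single case: "One or more subjects are withdrawn from the study (by investigator or subject request) following a Grade 3 AE" judged related.
- Items 6 and 7 are the 10% count rules for solicited local and solicited systemic reactions. Item 6 begins "Ten percent or more of subjects in any dose Arm experience any Grade 3 solicited local AE (lasting 48 hours or more"; item 7 has the same form.
- Item 9 applies the 10% rule to subjects who "experience the same or similar Grade 3 unsolicited AE" judged related.
- Item 8, the laboratory rule, is worded differently: "ten percent or more experience the same Grade 3 or higher laboratory abnormality". It also has a 30% limb for Grade 2 or higher.

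The single-subject rule in Section 12.10 refers to two or more "Grade 3 or greater AEs (solicited local/systemic or unsolicited; lasting 48 hours or more", and Section 12.12 (withdrawal for an adverse event) also covers Grade 3 and above. Section 12.9 says the PI "will make determinations regarding the presence and grading of AEs". Discretionary stops exist: item 10 of 12.9, a site-investigator decision under 12.10 that a safety issue "should pause administration of the study agent to a single subject or to all subjects in a specific group", and a sponsor provision that it "may also pause for an individual subject or entire group if a safety concern is identified".

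Grades come from Appendix D. Table 15 is used only for events that Appendix D does not list. For creatinine, Grade 3 runs up to 221.00 µmol/L in men and 162.43 µmol/L in women. Grade 4 needs a value above that limit together with a need for dialysis. Footnote 2 of the laboratory table allows Grade 4 when clinical signs or symptoms accompany the abnormality.

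**The concern.** A halting rule should never count a worse event for less than a milder one. Because the inclusive form appears in item 8, 12.10 and 12.12, its absence from items 3, 6, 7 and 9 reads as a deliberate limit. Counting Grade 4 events there would be an inference, not something the text says. If a Grade 4 reaction escapes both these items and the serious-event items, halting depends on judgement, which fixed thresholds are meant to replace. Safety is the primary objective, and up to 120 vaccine recipients (two arms of 60) could still be boosted.

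The creatinine row raises the same problem in another form: a value above the Grade 3 range can leave the count altogether.

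**Working it through.** The plan gives no operating figures for these rules, so there is none to reproduce. The check sets each Appendix D Grade 4 definition against items 1 to 9.

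**Step 1: which Grade 4 events are already caught.** Items 1 and 2 take any death or life-threatening SAE and any related SAE. Item 4 takes related hypersensitivity. Item 5 takes a local or solicited event leading to hospitalization, related fever above 40 °C, and injection-site necrosis. Item 8 takes graded laboratory values.

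**Step 2: what is left.** The SAE definition in Section 12.2 requires inpatient admission. An ER visit is not a criterion in itself, although the investigator may call the event medically important. If that call is not made:

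| Appendix D rows | Grade 4 route not caught | Count rule that misses it |
|---|---|---|
| Local, 5 of 6: pain, tenderness, pruritus, arm movement, erythema | ER visit without admission; for erythema, exfoliative dermatitis without necrosis | Item 6 |
| Systemic, 4 of 7: diarrhoea, headache, myalgia, arthralgia | ER visit without admission | Item 7 |
| Systemic, malaise (not in Table 14) | ER visit without admission | Item 9 |

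The other local row (induration) reaches Grade 4 only by necrosis, which item 5 takes. Grade 4 nausea/vomiting is tied to hypotensive shock and falls under item 1; urticaria is largely covered by item 4. The vital-sign rows name acute conditions likely to be SAEs. Unsolicited events graded by Table 15 reach Grade 4 only when intervention is needed to prevent death, which falls under item 1. The fixed clinical rule in 12.10 needs two or more events, so one such reaction does not trigger it either.

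**Step 3: effect on items 6 and 7.** Take five subjects with a qualifying Grade 3 reaction and one with a Grade 4 reaction of this kind. All events are related, last at least 48 hours and fall within 7 days of vaccination; the Grade 4 subject has no separate qualifying Grade 3 record.

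| Arm size | As written | With *or higher* |
|---|---|---|
| 60 (planned) | 5/60 = 8.3%, no halt | 6/60 = 10.0%, halt |
| 59 (236 re-consented × 1/4, assuming the 1:1:2 split holds) | 5/59 = 8.5%, no halt | 6/59 = 10.2%, halt |
| 54 (60 less 10% dropout) | 5/54 = 9.3%, no halt | 6/54 = 11.1%, halt |

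Six subjects in an arm of 60 with only Grade 4 reactions of this kind would not meet item 6 or 7 as written; six with Grade 3 would.

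**Step 4: item 3.** One subject withdrawn from the study after a related Grade 3 event halts it. One withdrawn after a related Grade 4 ER-visit reaction not judged serious does not.

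**Step 5: creatinine.** For a man without dialysis, signs or symptoms (illustrative values):

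- 200 µmol/L lies in 185.64–221.00, so it is Grade 3 and counts.
- 230 µmol/L exceeds 221.00 but lacks the dialysis condition, so it has no grade.

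Table 15 does not fill the gap, because Appendix D lists creatinine. The Grade 3 ceilings are 221.00/98 = 2.26 and 162.43/72 = 2.26 times the upper reference limits, so the ungraded values are well outside normal. In a 60-subject arm, five graded plus one ungraded value count as 8.3% rather than 10.0% under item 8. At its 30% limb, 17 plus one ungraded count as 17/60 = 28.3% rather than 18/60 = 30.0%. No other laboratory row has this gap: neutrophil Grade 3 is open-ended downward, and the haemoglobin row uses an and/or condition.

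**Step 6: who could still be protected.** Table 16 shows one booster row, at week 78. If all boosters are given within a week, 0% remain unboosted 7 days after the first. If they are spread evenly over the ±56-day visit window (112 days; an assumption), 1 − 7/112 = 93.75% remain.

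**The case against.** The strongest reply is that the residual is very narrow. The event must be related, Grade 4 without admission, and judged neither serious nor medically important. For items 6 and 7 it must also last 48 hours, fall within 7 days, carry no Grade 3 record, and arrive when the arm is one subject short of 10%. Section 3.5.2.1 reports 369 related local reactions in the main phase, 324 at Grade 1 and 45 at Grade 2, and all 37 Grade 3 events judged unrelated. Section 12.12 takes a subject off further vaccination after most related events of Grade 3 or above, item 10 and 12.10 allow discretionary stops, the DSMB may convene extra reviews, and no dose follows #4. All of this stands and sets the weight of the point. It does not supply a fixed rule for the event: 12.12 protects only the affected subject, and the other routes rest on judgement.

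Three narrower objections have force:

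- The 93.75% figure bears only on item 3. On an even spread, 60 × 7/112 = 3.75 subjects per arm have been dosed by then, too few for a six-subject count, and Table 16 points to the low end of the range.
- Table 14 solicits fatigue, which has no Appendix D row, while malaise has a row but no Table 14 entry. If the malaise row is meant to grade fatigue, that example moves from item 9 to item 7, where the gap is the same.
- Footnote 1 calls the laboratory limits guidelines, and the PI could grade a high creatinine by judgement. That is a workable reading, but the table does not state it, and the item 8 scenarios are in any case remote.

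**Conclusion.** The point holds. As worded, items 3, 6, 7 and 9 can count a related Grade 4 reaction for less than a Grade 3 one, and a creatinine above the Grade 3 ceiling can have no grade. The largest direct effect on a count rule is one subject per uncounted event, which decides the outcome only when an arm sits just below its threshold. Under item 3, a single event decides it.

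This rests on a literal reading of *Grade 3*, on the investigator not judging the event serious, and on the absence of a separate qualifying Grade 3 record. For creatinine it rests on there being no dialysis, no signs or symptoms, and no grade assigned by judgement. The practical consequence is low and limited to vaccination #4. For creatinine, what remains affected is item 8 and the severity summary in Section 14.2; the 12.10 subject halt no longer matters because no dose follows. How many subjects a halt could still protect depends on the pace of the booster roll-out, which the plan does not spell out. The point merits consideration as an inexpensive correction; it does not threaten the trial.

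**What to change.** In Section 12.9, write *Grade 3 or higher* in items 3, 6, 7 and 9, to match item 8, 12.10 and 12.12. In Appendix D, change the creatinine Grade 4 cells so that a value above 221.00 (men) or 162.43 (women) µmol/L, *or* a need for dialysis, is enough. Alternatively, leave creatinine Grade 3 open-ended upward when dialysis is not needed, as the neutrophil row does in its own direction. The sponsor and DSMB should choose between the two.

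The cost is six wording changes (four list items, two table cells), with no new data or visits. Halting becomes slightly more sensitive, by at most the number of subjects whose Grade 4 reaction or ungraded creatinine no current rule counts.
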